5 STATISTICAL CONSIDERATIONS

5.1 Primary and Secondary Outcomes

The primary outcome will be quantity of opiates used in terms of morphine equivalents. Secondary outcomes will include 24-hour composite pain scores, length of stay, respiratory

complications (pneumonia, atelectasis), venous thromboembolic event, myocardial infarction, nausea, vomiting, time to adequate oral intake (3 ounces each hour), and time to ambulation. Pain scores will be recorded by nursing staff using the universal pain assessment tool.

5.2 Sample Size and Power

The hypothesis for this study is that the 48 hour opioid consumption is different in one of the three groups. The study is powered to show a minimum clinically significant reduction of 30% in opioid usage compared to the control group (placebo group) 20% between the regular bupivacaine groups. According to our clinical audit, the mean (standard deviation) of amount of opioids used by patients undergoing these surgeries is 23.3 ± 14 mg morphine equivalents. Based on a two-sided alpha of 0.05 and 20% Type II error, 200 subjects need to be studied to disprove the null hypothesis. Additionally, to accommodate for attrition and missing data we plan to increase our sample size by 10%, a total of 219 subjects will be randomized.

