2.1 Primary Objective

- To determine if the use of long acting or regular acting local anesthetic for TAP block will have an effect on the use of opiates in patients undergoing bariatric surgery at MMC.

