3.2.2 Total Number of Study Sites/Total Number of Subjects Projected

- This prospective study will enroll patients at a single study site of MMC (Moses Division).
- We plan to enroll 219 patients/subjects (73 patients for each arm)

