5.3 Data analysis plan

Demographic and clinical characteristics such as (age, gender, type of surgery, medications, ASA status, co- morbidities, etc.) between the three study groups will be compared using one-way ANOVA or a non-parametric Kruskal Wallis test. Chi-square or Fisher's exact tests for categorical variables to ensure that randomization is appropriately implemented. The primary outcome of the study the opioid consumption at 48 hours will be analyzed using one-way ANOVA or a non-parametric Kruskal Wallis test. Mixed model analysis will be used to examine the effect of treatment on change in pain scores between the groups at 24 hours and 48 hours. All categorical variables such as, post-operative nausea and vomiting and any other clinically important medical conditions will be compared using chi-square or Fisher's exact tests.

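### Section 5.2 puts a 20% difference involving regular bupivacaine under its 80% power claim; at the stated SD, 200 evaluable patients support a pairwise 30% difference (about 82%) but not a pairwise 20% one (about 27-48%)

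*Combined protocol and SAP*

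**What the plan says.** Section 5.2 (Sample Size and Power) states a three-group hypothesis: "The hypothesis for this study is that the 48 hour opioid consumption is different in one of the three groups". It then says the study is powered for a "minimum clinically significant reduction of 30% in opioid usage compared to the control group (placebo group) 20% between the regular bupivacaine groups". The second half of that phrase lacks a connective and a comparator, and it refers to RB groups in the plural although there is one RB arm.

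The only variability figure is from a clinical audit: "the mean (standard deviation) of amount of opioids used by patients undergoing these surgeries is 23.3 ± 14 mg morphine equivalents". The size follows: "Based on a two-sided alpha of 0.05 and 20% Type II error, 200 subjects need to be studied to disprove the null hypothesis". Section 3.2.2 gives the randomized total: "We plan to enroll 219 patients/subjects (73 patients for each arm").

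Section 5.3 (Data analysis plan) says 48-hour opioid consumption "will be analyzed using one-way ANOVA or a non-parametric Kruskal Wallis test". It names no pairwise test for this outcome. Section 2.1 (Primary Objective) asks whether "use of long acting or regular acting local anesthetic for TAP block will have an effect on the use of opiates", so the RB arm is part of the main question.

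**The concern.** One sample size, one SD and one power figure are attached to two effects of different size, 30% and 20%. At a fixed SD, the number of patients needed for a pairwise comparison grows with the inverse square of the difference. Going from 30% to 20% of the same mean multiplies it by (30/20)² = 2.25. A sample that just suffices for the larger effect cannot also give 80% power for the smaller one as a pairwise contrast.

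The stake is interpretation. If an RB contrast is reported and is not significant, section 5.2 as worded invites the conclusion that RB has no effect, or that LB is no better than RB, because a 20% difference was supposedly covered at 80% power. A reader also cannot tell what the planned three-group test is powered for, since the three means are not given.

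**Working it through.** **Inputs from the plan.** Control mean 23.3 mg and SD 14 mg (section 5.2); two-sided alpha 0.05 and 80% power (section 5.2); 200 evaluable, so n = 200/3 = 66.7 per arm; 219 randomized, so 73 per arm if nobody is lost (section 3.2.2).

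**Assumptions.** The audit figures apply to the control arm at 48 hours (the plan gives no time window for them). The SD is 14 in every arm unless stated otherwise. No multiplicity adjustment, as none is stated.

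**1. The plan's own figure.** Section 5.2 does not say which test gave 200. For a pairwise 30% difference, 0.30 × 23.3 = 6.99 mg, and the normal approximation gives

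n = 2(1.96 + 0.842)² × 14² / 6.99² = 62.97, so 63 per arm or 189 in total.

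The noncentral t gives 64 per arm, or 192. One-way ANOVA gives 177 if one arm differs from the other two by 30%, and 228 or 234 for the patterns in step 4. None of these is 200. The pairwise 30% comparison is the nearest.

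**2. What 200 can detect pairwise.** The standard error of a difference is 14 × √(2/66.7) = 2.42 mg. The smallest difference with 80% power (noncentral t) is 6.84 mg, and 6.84/23.3 = 29% of the control mean. With 73 per arm it is 6.54 mg, or 28%.

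**3. Pairwise power** (noncentral t, noncentrality = difference / standard error).

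| Contrast | Difference (mg) | Power, 66.7 per arm | Power, 73 per arm | n per arm for 80% |
|---|---|---|---|---|
| 30% of control mean | 6.99 | 82% | 85% | 64 |
| 20% of control mean | 4.66 | 48% | 52% | 143 |
| LB 20% below RB, RB = 20.39 (LB is then 30% below control) | 4.08 | 39% | 42% | 187 |
| LB 20% below RB, RB = 18.64 (20% below control) | 3.73 | 33% | 36% | 223 |
| LB 20% below RB, RB = 16.31 (30% below control) | 3.26 | 27% | 29% | 291 |

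The expected 95% confidence interval half-width at 66.7 per arm is 4.80 mg, and 4.80/23.3 = 21% of the control mean. That is slightly wider than the 4.66 mg difference itself.

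**4. Power of the planned three-group ANOVA.** The noncentrality is λ = n Σ(mᵢ − m̄)² / 14², with 2 and 197 degrees of freedom. The mean patterns are assumptions.

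| Control / RB / LB (mg) | Σ(mᵢ − m̄)² | λ at 200 | Power at 200 | Power at 219 | N for 80% |
|---|---|---|---|---|---|
| 23.3 / 18.64 / 16.31 (RB 20%, LB 30% below control) | 25.33 | 8.62 | 74.5% | 78.5% | 228 |
| 23.3 / 20.39 / 16.31 (LB 30% below control, 20% below RB) | 24.66 | 8.39 | 73.2% | 77.3% | 234 |
| LB 30% below control, RB equal to control or to LB | 32.57 | 11.08 | 85% | 88% | 177 |
| 23.3 / 18.64 / 14.91 (LB 20% below RB, RB 20% below control) | 35.32 | 12.01 | 88% | 91% | 165 |
| 23.3 / 16.31 / 13.05 (LB 20% below RB, RB 30% below control) | 54.87 | 18.66 | 98% | 99% | 108 |

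**5. Does a significant ANOVA show the RB difference?** In 20,000 simulated normal trials with SD 14, ANOVA and RB versus control were both significant in about 45% under the first pattern. ANOVA and LB versus RB were both significant in about 37% under the second.

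**6. If the SD shrinks with the mean** (coefficient of variation 14/23.3 = 0.60; not stated in the plan). A 20% relative difference has standard error √((14² + 11.2²)/66.7) = 2.20 mg for a 4.66 mg difference. Power is about 56% on the raw scale and 63% on the log scale (60% and 67% with 73 per arm). If the 20% means 20 points of the control mean between RB and LB, raw/log power at 66.7 per arm is 66/74% with RB 10% and LB 30% below control, 77/84% at 20% and 40%, and 88/94% at 30% and 50%. Simulated three-group power in the first two patterns of step 4 rises to 87-88% for ANOVA and 82-92% for Kruskal-Wallis.

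**The case against.** The strongest reply is that the 80% belongs to the three-group test. Section 5.2 states a three-group hypothesis and ties the 200 to rejecting that null, and section 5.3 plans only ANOVA or Kruskal-Wallis. On that reading the 20% merely helps describe the assumed means, and the pairwise figures are beside the point. Power is then somewhere between a modest shortfall and none, depending on the means. This stands, and it is why the 27-48% is conditional on a pairwise reading. It does not rescue the wording, because section 5.2 says the study is powered to show the differences, and a significant three-group result does not show a particular 20% RB difference.

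A second reply is that a constant SD of 14 is doubtful at low means. The 27% figure pairs it with an LB mean of 13.05 mg, below the SD, for a quantity that cannot be negative. That is fair, but a shrinking SD still leaves a 20% relative difference at about 56-63%. Only readings with LB 40-50% below control reach 80%.

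A reader might infer more than the documents support:

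- **That the trial is too small for its primary test.** Omnibus power ranges from 73% to 98% across the patterns shown at SD 14, and the plan does not say which pattern it assumes.
- **That a calculation error has been shown.** The 200 could not be reproduced, but the test and means behind it are not stated, and the clause is visibly incomplete.
- **That the 30% is specifically for LB.** Section 5.2 does not name the block it applies to.

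**Conclusion.** The concern holds in a conditional form. At the stated mean and SD, two-sided 0.05 and 200 evaluable, the sample supports a 30% difference from control as a single unadjusted pairwise comparison. It does not support a pairwise 20% difference at 80% power under any of the readings computed at SD 14, even with all 219 evaluable (29-52%).

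If the 20% is part of the mean pattern for the three-group test, the power of that test cannot be determined from the plan. At SD 14 the two patterns that combine LB 30% below control with a 20% RB effect fall 5 to 7 points short of 80%.

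The conclusion rests on reading the clause as a claim about a 20% difference involving RB, on a common SD of 14, and on the audit figures representing 48-hour use in the control arm. Confidence is moderate because the clause is incomplete. This should be fixed, but it does not affect the validity of the primary test.

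**What to change.** Keep 219 patients and the primary test.

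In section 5.2:

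1. State what the 20% refers to (which arms, and a percentage of which mean), the three assumed means, the SD assumption, and the test from which 200 was obtained. Give the resulting power of that test.
2. If the 20% is a pairwise contrast, remove the 80% power claim for it and state its actual power at SD 14: about 48% for 20% of the control mean, or about 27-39% for LB 20% below RB. If it is part of the three-group mean pattern, these figures do not apply and item 1 suffices.
3. Describe the roughly 82% for the 30% difference as the power of a single unadjusted pairwise comparison with control, not of the ANOVA or Kruskal-Wallis test.

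In section 5.3:

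4. Report any RB contrasts as estimates with 95% confidence intervals (expected half-width about 4.8 mg, 21% of the control mean), labelled as unadjusted secondary estimates, so that a non-significant one is not read as no difference.

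The cost is protocol text and a few extra reported estimates, with no added patients. The stated power becomes less favourable, and the sponsor must commit to explicit means and an SD assumption.

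### Section 5.2 claims 80% power at 200 subjects for the three-group null without giving the test or the arm means; readings that use both its percentages, with LB 30% below control, give ANOVA power of about 73–74.5%

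*Combined protocol and SAP*

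**What the plan says.** Section 5.2 of the combined protocol and SAP sets a three-group hypothesis: "The hypothesis for this study is that the 48 hour opioid consumption is different in one of the three groups". It then gives two effect sizes. The first reads "The study is powered to show a minimum clinically significant reduction of 30% in opioid usage compared to the control group (placebo group"; the second, straight after it, reads "20% between the regular bupivacaine groups". The only location and spread figures come from a clinical audit: "the mean (standard deviation) of amount of opioids used by patients undergoing these surgeries is 23.3 ± 14 mg morphine equivalents". The conclusion is: "Based on a two-sided alpha of 0.05 and 20% Type II error, 200 subjects need to be studied to disprove the null hypothesis". For attrition, "we plan to increase our sample size by 10%, a total of 219 subjects will be randomized", which section 3.2.2 splits into 73 per arm.

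Section 5.3 fixes the primary analysis: "The primary outcome of the study the opioid consumption at 48 hours will be analyzed using one-way ANOVA or a non-parametric Kruskal Wallis test". It gives no pairwise primary test and no multiplicity rule. Section 5.2 names no test or formula for the 200 and gives no assumed mean for either block arm.

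**The concern.** The 20% Type II error is attached to rejecting the three-group null, so it should describe the omnibus test in section 5.3. The power of that test depends on all three means. An RB mean lying between the other two adds little to the between-group variation, while the test still spends two numerator degrees of freedom. A sample size that suits one two-group comparison can therefore fall short for the omnibus test.

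This matters for reading a non-significant primary result. If the chance of missing the intended pattern is nearer 26% than 20%, such a result is weaker evidence of no difference than the protocol implies. The point concerns the power claimed for the primary test itself, not the power of any single 20% contrast.

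**Working it through.** **Inputs.** From section 5.2: control mean 23.3 mg, SD 14 mg, 30% and 20% differences, two-sided alpha 0.05, 80% power, 200 evaluable, 219 randomized. Assumptions added here: the 30% belongs to LB against control, data are normal, and SD 14 holds in every arm. The 30% difference is 0.30 × 23.3 = 6.99 mg, so LB = 16.31 mg.

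**Step 1: the plan's own 200.** Two-group formula: n per arm = 2(1.960 + 0.842)² × 14² / 6.99² = 62.97, rounded up to 63.

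- Normal version: 63 × 3 = 189.
- t-test version: 64 × 3 = 192.
- Normal version divided by the rank-test efficiency 0.955: 62.97 / 0.955 = 65.9, so 66 × 3 = 198.
- t-test version divided by 0.955: 64 / 0.955 = 67.0, so 67 × 3 = 201.
- Adding 10% to 66: 66 × 1.1 = 72.6, rounded up to 73 per arm, or 219. By comparison, 200 × 1.1 = 220.

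The plain two-group calculation is thus 4–6% below 200. The rank-test version brackets 200 and leads to 219, but the 0.955 factor appears nowhere in the documents. The t-test power for the 30% difference is 81.2% at 66 per arm and 81.8% at 67.

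**Step 2: the planned omnibus test.** Noncentral F with 2 and N − 3 degrees of freedom, and λ = (N/3) × Σ(mean − grand mean)² / 14².

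Worked example, means 23.3 / 18.64 / 16.31: the grand mean is 19.417 and the sum of squares is 25.33, so λ = (200/3) × 25.33 / 196 = 8.62. The critical F(2, 197) is 3.04, and power is 74.5%.

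| Reading (control 23.3 throughout) | RB | LB | Power at 200 | Power at 219 | N for 80% |
|---|---|---|---|---|---|
| RB 20% below control | 18.64 | 16.31 | 74.5% | 78.5% | 227–228 |
| LB below RB by 20% of the control mean | 20.97 | 16.31 | 74.5% | 78.5% | 227–228 |
| LB 20% below RB | 20.39 | 16.31 | 73.2% | 77.3% | 233–234 |
| 20% ignored: RB equal to control | 23.3 | 16.31 | 85.0% | 88.2% | 177 |
| 20% ignored: RB equal to LB | 16.31 | 16.31 | 85.0% | 88.2% | 177 |
| RB 30% below control, LB a further 20% below RB | 16.31 | 13.05 | 97.7% | 98.6% | 107–108 |

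The higher figure in each N range rounds up to three equal arms. With LB held at 16.31, the least favourable RB is midway (19.8 mg), with 72.8% at 200. On a grid of whole percentages, power at 200 is below 80% for every RB reduction from 5% to 25% of control.

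**Step 3: Kruskal-Wallis and other distributions.** These are simulations of 4,000 runs at 66–67 per arm, for the patterns with RB at 18.64 and 20.39.

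- Normal data, SD 14: Kruskal-Wallis 70–73%.
- Gamma data with the audit's coefficient of variation (14 / 23.3 = 0.60) in every arm: ANOVA 86–89%, Kruskal-Wallis 82–83%.
- Gamma data with SD 14 in every arm: ANOVA 72–76%, Kruskal-Wallis 90–92%.

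**The case against.** The strongest reply is that the protocol's figures do not determine the omnibus power. No RB mean is stated and the reference for the 20% is unclear. The hypothesis wording can be read as one group differing from the other two; with the stated 30%, that gives 85%, and 177 subjects would suffice. This stands as a limit on the finding: 73–74.5% holds only once an RB mean is supplied. But the three readings that use both percentages with LB at 30% below control agree to within 1.3 points. The readings above 80% either leave the stated 20% unused or put LB 44% below control (1 − 13.05 / 23.3), which section 5.2 does not describe.

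The second reply is that the spread is uncertain. SD 14 is one audit figure, not stated to apply to the block arms. A common SD of 13 would give about 80–81% at 200, and step 3 shows power above 80% under some skewed distributions. This also stands. It does not rescue the printed 80%, because section 5.2 offers no other SD and no distribution from which that figure would follow.

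A reader might also infer that the 200 was certainly obtained by tripling a two-group calculation. The documents do not support that. The match needs an unstated rank-test factor, and an ANOVA with RB 4% or 26% below control would need 201. Section 5.2 states neither of those RB values, but it names no method that would rule them out.

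**Conclusion.** The concern holds in a limited form. Section 5.2 assigns 80% power to a three-group test without the means or method that would produce it. Under the readings that use both percentages with LB 30% below control, Type II error at 200 evaluable is 25.5–26.8% (1 − 0.745 to 1 − 0.732), so power is about 5.5 to 7 points below the claim. Even with no attrition it stays 1.5 to 2.7 points short.

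These sizes rest on normal data, SD 14 in every arm, ANOVA, and the 30% belonging to LB. It would be tempting to conclude that the trial is underpowered outright. The documents do not support that, because the RB mean is unstated and some readings or distributions exceed 80%. What they show is a power claim that cannot be traced to its stated inputs and is too high on the readings that use both percentages as described.

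**What to change.** Keep 219 randomized and change section 5.2 only:

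1. The sponsor confirms which meaning of the 20% was intended, and section 5.2 states the three assumed means, the SD and the test behind the 200.
2. State that 200 evaluable gives about 81–82% power for one unadjusted two-group comparison of a 30% reduction (6.99 mg, SD 14).
3. Replace the 20% Type II error for the three-group test with the value for the stated means. This is about 25–27% if LB is 30% below control and RB lies at 18.6–21.0 mg. If the sponsor confirms a different pattern, give the power for that pattern. If a smaller SD in the block arms or a skewed distribution is assumed, state it beside the figure.

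The cost is wording, plus the sponsor's confirmation of the 20%. No patients, arms, endpoints or analyses change. The downside is a stated power about 6 points less favourable under the readings above.

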5.3 Data analysis plan

Demographic and clinical characteristics such as (age, gender, type of surgery, medications, ASA status, co- morbidities, etc.) between the three study groups will be compared using one-way ANOVA or a non-parametric Kruskal Wallis test. Chi-square or Fisher's exact tests for categorical variables to ensure that randomization is appropriately implemented. The primary outcome of the study the opioid consumption at 48 hours will be analyzed using one-way ANOVA or a non-parametric Kruskal Wallis test. Mixed model analysis will be used to examine the effect of treatment on change in pain scores between the groups at 24 hours and 48 hours. All categorical variables such as, post-operative nausea and vomiting and any other clinically important medical conditions will be compared using chi-square or Fisher's exact tests.

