3.3 Study Population

3.3.1 Inclusion Criteria

- 1) Obese patients undergoing bariatric surgery (LSG or LRYGB)
- 2) Patients 18 years of age and older
- 3) Surgical treatment between 01/01/2018 and 12/31/2018 over a 1 year period

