5.4 Randomization

The research data collector will be responsible for the randomization. Subjects will be randomized in a 1:1:1 ratio to receive LB as a TAP block infiltration or RB as a TAP block infiltration or no TAP block infiltration.

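### The primary test is unadjusted although procedure, age and weight/BMI are already recorded, which forgoes precision at no saving; and baseline p-values are used to check randomization, which they cannot do

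*Combined protocol and SAP*

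**What the plan says.** - **Primary analysis (section 5.3).** "The primary outcome of the study the opioid consumption at 48 hours will be analyzed using one-way ANOVA", with a Kruskal-Wallis test as the alternative. No covariate is named, and no rule is given for choosing between the two tests.
- **Baseline comparisons (section 5.3).** The listed characteristics are "age, gender, type of surgery, medications, ASA status, co- morbidities, etc". They are to be tested across arms by ANOVA or Kruskal-Wallis, and, for categorical items, by "Chi-square or Fisher's exact tests for categorical variables to ensure that randomization is appropriately implemented". BMI is not in the list.
- **Allocation (section 5.4).** "Subjects will be randomized in a 1:1:1 ratio". The section also says who is responsible. It gives no stratification factor, block scheme or sequence method.
- **Population and data (sections 3.3.1 and 9.1.2).** Both laparoscopic sleeve gastrectomy (LSG) and laparoscopic Roux-en-Y gastric bypass (LRYGB) are eligible. The data collection sheet has fields for procedure, age and weight/BMI.
- **Related objective (section 2.2).** Associations of demographic factors with outcomes are a secondary objective. Section 5.3 gives no method for it.

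**The concern.** Two different operations are combined in one outcome, and three plausible predictors of that outcome are already being collected. A one-way test leaves whatever variation they explain in the error term. A pre-specified adjusted model would remove it, for three degrees of freedom and no extra data. If the covariates are prognostic, the confidence intervals for the arm differences are wider than they need to be.

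The baseline tests are a separate weakness that needs no assumption about prognosis. Under correct randomization every baseline difference is due to chance, so a small p-value does not reveal a fault and a large one does not certify the process. The plan does not say what follows a significant result.

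**Working it through.** **Inputs from the documents.** Control mean 23.3 mg and SD 14 mg morphine equivalents, two-sided alpha 0.05, 80% power, 200 evaluable patients, and a 30% reduction against control plus a 20% figure whose reference group is unclear (section 5.2); 73 per arm (section 3.2.2).

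**Inputs assumed.** R², the share of within-arm outcome variance explained by procedure, age and BMI together: 0.05 to 0.20. Bypass share 20% to 50%. Sleeve-bypass difference in opioid use 4 to 8 mg. The documents give none of these.

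**1. The plan's own figure.** For the 30% contrast alone, the difference is 0.30 × 23.3 = 6.99 mg. The normal formula gives 63 per arm (189 in total) and the t-test version 64 per arm (192), so these do not reproduce 200. At 200/3 per arm this pairwise contrast has 82.2% power.

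**2. Unadjusted omnibus power at 200.** Take one reading of section 5.2: regular bupivacaine 20% and liposomal bupivacaine 30% below control.
- Means: 23.3; 0.8 × 23.3 = 18.64; 0.7 × 23.3 = 16.31. Grand mean 19.417.
- Sum of squared deviations: 15.080 + 0.603 + 9.651 = 25.335.
- Noncentrality: λ = (200/3) × 25.335 / 14² = 8.617.
- Noncentral F with 2 and 197 degrees of freedom: power 74.5%.

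**3. Adjusted omnibus power.** Residual SD = 14 × √(1 − R²), λ = 8.617 / (1 − R²), and 2 and 194 degrees of freedom. The last column is the 95% half-width for a pairwise difference, 1.96 × SD × √(2/66.67).

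| Assumed R² | Residual SD (mg) | λ | Omnibus power | Half-width (mg) |
|---|---|---|---|---|
| 0 (unadjusted) | 14.00 | 8.617 | 74.5% | 4.75 |
| 0.05 | 13.65 | 9.071 | 76.7% | 4.63 |
| 0.10 | 13.28 | 9.575 | 79.1% | 4.51 |
| 0.20 | 12.52 | 10.772 | 83.9% | 4.25 |

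Equivalently, an adjusted analysis of 200 × (1 − R²) = 190, 180 or 160 patients matches an unadjusted analysis of 200. If R² were 0, spending the three degrees of freedom would take power from 74.5% to 74.4%.

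**4. Procedure alone.** R² = p(1 − p)d²/SD². With 30% bypass and a 4 mg difference: 0.3 × 0.7 × 16 / 196 = 0.017, which moves omnibus power only from 74.5% to 75.2%. With 8 mg: 0.3 × 0.7 × 64 / 196 = 0.069.

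**5. Chance imbalance in procedure mix without stratification.** The 95% range for the difference in bypass share between two arms of 67 is ±1.96 × √(2p(1 − p)/67), or ±14, ±16 and ±17 percentage points at 20%, 30% and 50% bypass. The effect on the comparison is small: a 10-point imbalance shifts it by 0.10 × 4 = 0.4 mg, or 0.8 mg if the operations differ by 8 mg. The standard error at 73 per arm is 14 × √(2/73) = 2.3 mg.

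**6. Baseline tests.** Section 5.3 names six items. Treated as independent tests at 0.05: 1 − 0.95⁶ = 26.5% chance of at least one p < 0.05 under perfect randomization.

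**7. Scale.** Mean/SD = 23.3/14 = 1.66. A normal distribution with these values would put about 5% of patients below zero, which is impossible for opioid use. Some right skew is therefore likely, and the scale of a linear model needs to be stated.

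**The case against.** The case for leaving the plan alone is substantial. After randomization, an unadjusted one-way ANOVA keeps its type I error. The SD of 14 mg comes from a pooled audit figure, so any variation due to procedure, age or size is already inside it, and omitting covariates takes nothing from the planned power. Nothing in the documents shows that these covariates predict 48-hour opioid use. Procedure alone may explain about 2% of the variance, and a chance imbalance in it would move the comparison by well under one standard error. All of this stands, and it limits the point to a missed gain.

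A reader might infer four stronger things that the documents do not support:
- **That randomization is unstratified.** Section 5.4 is silent on the method. It can only be said that no stratification is specified.
- **That baseline tests replace adjustment, or will trigger unplanned adjustment.** Section 5.3 says neither. It leaves the consequence of a significant result unstated.
- **That the baseline tests cost precision.** They do not; their fault is that they do not answer the question put to them.
- **That the trial is underpowered and the missing covariates are the cause.** The 74.5% rests on one reading of an ambiguous sentence in section 5.2. Omnibus power at 200 is 73.2% if liposomal bupivacaine is 30% below control and 20% below regular bupivacaine, and 85.0% if regular bupivacaine equals control. The covariates do not cause a shortfall under any reading.

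What the objection leaves untouched is that the covariates are already collected, that adjusting for them costs almost nothing even if they prove uninformative, and that the baseline tests cannot do what section 5.3 asks of them.

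**Conclusion.** The point holds as a minor one: a nearly free improvement, not an error that invalidates the analysis. The textual facts are certain: no covariates are named in the primary analysis, no stratification is specified, and baseline tests are given a purpose they cannot serve. The size of the gain is not certain. It is about 2 percentage points of omnibus power at R² = 0.05, 5 at 0.10 and 9 at 0.20, for 200 patients and means of 23.3, 18.64 and 16.31 mg. Both R² and that reading of the effect sizes are assumptions. The 26.5% figure assumes six independent tests; correlated variables, or more tests under the open-ended list, would change it.

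**What to change.** **Section 5.3, primary analysis.** Replace the open choice between ANOVA and Kruskal-Wallis with one named linear model (ANCOVA) for 48-hour opioid use, with arm, procedure type, age and BMI as pre-specified terms. State the outcome scale in advance, because skew is likely. Keep any rank test as a sensitivity analysis; Kruskal-Wallis cannot take covariates, so it cannot remain an equal alternative.

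**Section 5.3, baseline.** Present baseline characteristics by arm descriptively, without p-values, and add BMI to the list.

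**Section 5.4 (secondary).** If allocation has not begun, stratify the list by LSG/LRYGB with permuted blocks and keep procedure in the model. If it has begun, leave the allocation as it is; the model and table changes can still be made before any unblinded analysis.

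**Cost.** Three degrees of freedom, a few sentences in section 5.3 and, where still possible, one factor in the allocation list. No new data are needed.
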